The preceding table summarizes the planned dose levels. The primary objective of the dose escalation component of the study is to define the maximum tolerated dose (MTD) of the triple combination of dabrafenib, trametinib, and AT13387. Dose escalation will follow a standard 3+3 design beginning in dose level 1. The doses of dabrafenib and trametinib for Dose Level 1 were selected based upon the results of the phase I study showing excellent tolerability and safety, and that this combination appears to be associated with a reduced incidence and severity of *some* of the toxic effects of monotherapy with either a BRAF or MEK inhibitor., as well as excellent clinical activity. (Flaherty *et al.* 2012) Of note, the first dose cohort (dose level 1) incorporates a trametinib dose of 1 mg daily as opposed to the FDA-approved dose of 2 mg daily. This dose was chosen due to the theoretical overlapping ocular toxicity of trametinib and AT13387.

It is conceivable that additional cohorts may be necessary to pick an optimal treatment regimen with the three agents. As such, if toxicity is seen at a dose level where dose modification is necessary and the prior, lower dose level was treated without DLT, then additional dose cohorts between the two dose levels will be considered (see section 5 for details of this process). If the toxicity is determined to be related to dabrafenib (i.e. palmar-plantar erythrodysesthesia syndrome, arthralgia) then the dose of dabrafenib will be reduced first to 75 mg BID and then increased to 100 mg BID if that first dose level is tolerated. If the toxicity is determined to be related to trametinib, then the dose of trametinib will be reduced to 1 mg QD (if a dose higher than 1 mg QD is being evaluated in the dose cohort) and then increased to 1.5 mg QD if that first dose level is tolerated. If the toxicity is determined to be related to AT13387 then the dose will be reduced by 1 dose cohort. At the end of the planned enrollment to the phase 1 portion of the study, a complete review of the PK data and safety will occur before cohort expansion at the MTD.

TABLE OF CONTENTS

SCHEMA.....	3
1. OBJECTIVES	6
1.1 Phase I Objectives.....	6
2. BACKGROUND	6
2.1 BRAF mutant melanoma	6
2.2 CTEP Agents	7
2.3 Rationale	37
2.4 Correlative Studies Background	39
3. PATIENT SELECTION	40
3.1 Eligibility Criteria	40
3.2 Exclusion Criteria	42
3.3 Inclusion of Women and Minorities	45
4. REGISTRATION PROCEDURES	46

1. OBJECTIVES

1.1 Phase I Objectives

1.1.1 Primary Objective

1.1.1.1 To determine the maximum tolerated dose (MTD), toxicity, and safety profile of AT13387 given weekly in combination with dabrafenib and trametinib in patients with BRAF-mutant metastatic or unresectable solid tumors.

1.1.2 Secondary Objectives

1.1.2.1 To obtain preliminary estimates of the objective response rate (ORR) and progression-free survival (PFS) and document the 6-month PFS and 1-year overall survival (OS) of patients with BRAF-mutant metastatic or unresectable melanoma treated with AT13387 given weekly in combination with dabrafenib and trametinib.

1.1.2.2 To describe the pharmacokinetics of treatment with dabrafenib, trametinib, and AT13387.

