3. PATIENT SELECTION

3.1 Eligibility Criteria

3.1.1 Patients must have histologically confirmed, BRAF-mutant (V600E/K) solid tumor (molecularly confirmed using Cobas assay or a comparable FDA-approved assay) that is metastatic or unresectable, have received and tolerated prior BRAF or BRAF and MEK inhibitor (BRAF targeted) therapy at full dose or not previously received BRAF targeted therapy, and for which standard curative measures do not exist or are no longer effective.

- If test at CLIA-certified lab used a non-FDA approved method, information about the assay must be provided. (FDA approved tests for BRAF V600 mutations in melanoma include: THxID BRAF Detection Kit and Cobas 4800 BRAF V600 Mutation Test).

3.1.2 Patients must have measurable disease, defined as at least one lesion that can be accurately measured in at least one dimension (longest diameter to be recorded for non-nodal lesions and short axis for nodal lesions) as ≥ 20 mm with conventional techniques or as ≥ 10 mm with spiral CT scan, MRI, or calipers by clinical exam. See Section 11 for the evaluation of measurable disease.

3.1.3 Prior therapy is allowed. Patients may have received any number of prior lines of therapy, including treatment with a BRAF and/or MEK inhibitor.

3.1.4 All prior anti-cancer treatment-related toxicities must be less than or equal to Grade 1 according to the Common Terminology Criteria for Adverse Events version 5 (CTCAE version 5.0; NCI,2017) at the time of enrollment. **A notable exception** are endocrinopathies caused by immune checkpoint inhibitors that are appropriately treated with medical management (e.g. hormone replacement therapy, anti-diabetic agents)

3.1.5 Age ≥ 18 years. Because no dosing or adverse event data are currently available on the use of AT13387 in combination with dabrafenib and trametinib in patients <18 years of age, children are excluded from this study, but will be eligible for future pediatric trials.

3.1.6 ECOG performance status ≤ 1 (Karnofsky $\geq 70\%$, see Appendix A).

3.1.7 Life expectancy of greater than 3 months.

3.1.8 Patients must have normal organ and marrow function as defined below:

- leukocytes	$\geq 3,000/\text{mcL}$
- absolute neutrophil count	$\geq 1,200/\text{mcL}$
- hemoglobin	$\geq 9 \text{ g/dL}$ (patients may be transfused to this level)
- platelets	$\geq 100,000/\text{mcL}$

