If $\geq 2/3$ or $\geq 2/6$ patients at dose level 1 experience dose limiting toxicities, dose level -1 will be enrolled. If dose level -1 proves too toxic, the study will stop.	Dose escalation will be stopped. The MTD will be one dose below this dose level. Three (3) additional patients will be entered at the next lower dose level if only 3 patients were treated previously at that dose.

The following table shows the probability of escalating the dose for various true, but unknown, rates of unacceptable toxicity.

True DLT Rate	Probability of Dose Escalation
0.10	0.91
0.20	0.71
0.30	0.49
0.40	0.31
0.50	0.17
0.60	0.08

A patient will be replaced if determination of DLT cannot be adequately assessed because of rapid disease progression or if treatment is stopped during the first cycle of therapy for reasons other than toxicity.

When the MTD had been determined, a total of 14 patients will be enrolled in an expansion cohort of patients with BRAF-mutant advanced solid tumors to obtain preliminary toxicity and efficacy estimates. Patients treated at the MTD during the dose escalation phase may be included in the expansion cohort. Toxicity and efficacy rates will be summarized with 90% exact binomial confidence intervals. For a sample of size 14, the confidence intervals will be no wider than 0.48.

The table below summarizes the probabilities of observing at least one patient with a severe or unexpected toxicity in the expansion cohort for a range of incidence rates.

True Incidence of Unexpected or Severe Toxicity	Probability of Observing One or More Patients with Toxicity among 14
0.01	0.13
0.03	0.35
0.05	0.51
0.08	0.69
0.09	0.73
0.10	0.77
0.15	0.90

Secondary endpoints that will be assessed for the 14 patients treated at the MTD are: objective response rate, progression-free survival (PFS), 6-month PFS, and 1-year overall survival (OS).

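### The efficacy objective is for melanoma, but the plan estimates it in patients with any BRAF-mutant solid tumour, with no melanoma analysis set

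*Combined protocol and SAP*

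**What the plan says.** Section 1.1.2.1 aims to estimate ORR and PFS and to "document the 6-month PFS and 1-year overall survival (OS) of patients with BRAF-mutant metastatic or unresectable melanoma". The patients it covers are those with "melanoma treated with AT13387 given weekly in combination with dabrafenib and trametinib". The primary objective, in section 1.1.1, is instead set "in patients with BRAF-mutant metastatic or unresectable solid tumors". Eligibility follows the primary objective. Section 3.1.1 begins "Patients must have histologically confirmed, BRAF-mutant (V600E/K) solid tumor", with no restriction on histology, and admits patients who "have received and tolerated prior BRAF or BRAF and MEK inhibitor (BRAF targeted) therapy at full dose or not previously received BRAF targeted therapy".

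Section 13.1 states that "a total of 14 patients will be enrolled in an expansion cohort of patients with BRAF-mutant advanced solid tumors" and then lists the four efficacy endpoints under the words "Secondary endpoints that will be assessed for the 14 patients treated at the MTD are". Its one precision statement is "For a sample of size 14, the confidence intervals will be no wider than 0.48". Section 13.3 repeats the response and survival analyses without naming a tumour type.

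**The concern.** The objective and the analysis meant to answer it name different populations. The objectives themselves also disagree: safety is for solid tumours, efficacy for melanoma only. An all-tumour estimate answers 1.1.2.1 only if all 14 patients have melanoma or if outcomes do not depend on tumour type. The plan secures neither, and the protocol's background shows that response to dabrafenib plus trametinib differs widely between tumour types.

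A smaller difference is that 1.1.2.1 covers melanoma patients treated with the combination at any dose level, whereas 13.1 is limited to the MTD.

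At stake is the meaning of the trial's only efficacy figures. If the population is left open, the choice between a pooled and a melanoma figure, and between the MTD and all doses, could be made after responses are known in an open, single-arm trial.

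**Working it through.** **1. Is there a melanoma analysis anywhere?** The sections that could supply one do not:

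- 3.1.1: histology is confirmed at entry, but any V600E/K solid tumour qualifies.
- 11.1.1: evaluability for response does not depend on tumour type.
- 13.1: the endpoint definitions name no tumour type.
- 13.2: there is no melanoma quota or minimum.
- 13.3: subset analyses are planned, but that paragraph concerns prior therapy (named immunotherapy agents) and on-study features such as dose reductions. Tumour type is not listed.
- 10, footnote j: baseline brain imaging is required for melanoma patients. This is a procedure, not an analysis.

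**2. The plan's own precision figure.** The 90% exact (Clopper-Pearson) interval for x responses in n has lower limit Beta(0.05; x, n−x+1) and upper limit Beta(0.95; x+1, n−x). At n=14 the widest interval is at x=7: 0.264 to 0.736, width 0.473. The stated bound of 0.48 reproduces.

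**3. Precision for the objective's population.** The documents do not give the number of melanoma patients among the 14, so a range is shown. The Kaplan-Meier column assumes no censoring before the landmark: SE of log(−log S) = √((1−S)/(nS))/|ln S|, z = 1.645, maximum over S = x/n. Censoring would widen these intervals.

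| Melanoma patients | Max 90% exact width, ORR | Max 90% log(−log) width, 6-month PFS or 1-year OS |
|---|---|---|
| 14 | 0.473 | 0.422 |
| 12 | 0.509 | 0.453 |
| 10 | 0.555 | 0.491 |
| 7 | 0.646 | 0.576 |
| 5 | 0.734 | 0.663 |

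At 13 melanoma patients the ORR width is 0.489, so the 0.48 bound fails for melanoma as soon as one of the 14 has another tumour.

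**4. How far a pooled ORR could sit from the melanoma ORR.** Pooled ORR = (k·m + (14−k)·r)/14, where k is the number with melanoma, m the melanoma ORR and r the ORR in the rest.

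- m: 50% and 76% are the doublet rates in section 2.3 (trametinib 1 mg and 2 mg). The documents give no doublet rate after prior BRAF-inhibitor exposure, which 3.1.1 allows, so 12% and 30% are added as assumptions.
- r: 12% for colon cancer on the doublet (2.1), or 5/13 = 38% for papillary thyroid cancer on dabrafenib alone (2.2.2.2). The latter is approximate, because the tumour counts given there (7+13+1+1 = 22) do not sum to the stated 18.
- k: 10 and 12 are assumptions.

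| k, remainder | m=12% | m=30% | m=50% | m=76% |
|---|---|---|---|---|
| 10, colon 12% | 12.0% (0.0) | 24.9% (−5.1) | 39.1% (−10.9) | 57.7% (−18.3) |
| 12, colon 12% | 12.0% (0.0) | 27.4% (−2.6) | 44.6% (−5.4) | 66.9% (−9.1) |
| 10, thyroid 38% | 19.6% (+7.6) | 32.4% (+2.4) | 46.7% (−3.3) | 65.3% (−10.7) |

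Each cell is the pooled ORR, with its difference from m in points. For example, (10×0.76 + 4×0.12)/14 = 8.08/14 = 0.577.

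The largest half-width at n=14 is 0.473/2, about 24 points, and every shift in the table is smaller. No shift is computed for PFS or OS, because the documents give no doublet PFS or OS outside melanoma.

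**The case against.** The strongest reply is that this is one stray word. The primary objective, eligibility and section 13.1 all say solid tumours, and replacing melanoma in 1.1.2.1 would restore agreement. That may be what was intended, but the documents do not say so. The background rationale is mostly about melanoma, so the other reading is also plausible, and the sponsor has to choose.

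The second reply is that little hangs on it: the estimates are secondary and preliminary, no test or go/no-go rule uses them, and the illustrated shifts fall within the interval half-width. This is right and limits the weight of the point. It does not remove it, since an imprecise estimate still needs a stated population.

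Third, the shifts rest on assumed case mixes and rates, and even their sign changes with those choices. Section 2.1 also reports responses in nearly half of papillary thyroid patients on vemurafenib. Taking 50% for the remainder at k=10, the four shifts become about +11, +6, 0 and −7 points. The shifts are therefore illustrations only.

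Two wording points also stand. Section 13.1 speaks once of an additional 14 patients and once of a total of 14 that may include escalation patients. On the first reading up to 6+14 = 20 could be treated at the MTD, with a maximum exact width of 0.40. Section 13.3 carries no MTD limit, so the plan is not uniformly MTD-only. Neither supplies a melanoma analysis.

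**Conclusion.** The concern holds. As written, the plan produces an all-tumour estimate for an objective that asks for a melanoma estimate, and no section bridges the two. The mismatch follows from the text alone and needs no assumption.

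Its numerical size is conditional on the case mix and response rates. In the scenarios tabulated, the pooled ORR lies between 18 points below and 8 points above the melanoma ORR. The trial could not detect shifts of that size. The stated 0.48 bound is correct for 14 patients but does not carry over to a melanoma subset of 13 or fewer. The MTD, the sample size and the safety analyses are untouched. This should be corrected, but it does not threaten the trial's primary purpose.

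**What to change.** Choose one population and state it consistently in 1.1.2.1, 13.1 and 13.3.

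- **Option A, if melanoma is meant.** Report the four endpoints in melanoma patients treated at the MTD as the answer to 1.1.2.1, with the all-tumour MTD result as supportive. Melanoma patients from all dose levels may be added as a second supportive set, since 1.1.2.1 is not limited to the MTD. State that the 0.48 bound applies only at n=14, and that the maximum 90% exact width for ORR is 0.51 at n=12, 0.56 at n=10, 0.65 at n=7 and 0.73 at n=5. State also that PFS and OS carry their own Kaplan-Meier intervals.
- **Option B, if all tumours are meant.** Widen 1.1.2.1 to BRAF-mutant solid tumours treated at the MTD and report the four endpoints by tumour type, descriptively only, since some groups may hold very few patients.

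The same edit should settle whether 13.3 is limited to the MTD.

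The cost is wording in three sections and one or two tables. No new data are needed, because histology is confirmed at entry. Option A gives wider intervals, and without a minimum melanoma number the set could be small. The optional all-dose set mixes doses, so it should stay supportive.

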2. BACKGROUND

2.1 BRAF mutant melanoma and other solid tumors

The incidence of melanoma has dramatically risen over the past several decades and in 2013, an estimated 76,690 new cases and 9,480 deaths are expected in the United States. (Seigel *et al.*, 2013) As a result, melanoma is now the 5th and 7th most common malignancy in the US among men and women, respectively. The prognosis for patients with metastatic melanoma is poor, though is dramatically different if the disease is limited to subcutaneous and/or lymph nodes (M1a), if the lungs are the only site of visceral metastasis (M1b), or if other sites of visceral metastasis are identified and/or if the lactate dehydrogenase (LDH) level is elevated (M1c). In particular, the 1-year survival rates of M1a, M1b, and M1c are 68%, 58%, and 38% respectively. (Balch *et al.*, 2009) Still, melanoma typically disseminates widely, and frequently involves sites that are uncommon in other cancers, such as the GI tract and the skin. Treatment options for stage IV melanoma have traditionally been extremely limited, with only dacarbazine (DTIC) and high-dose interleukin 2 (HD IL-2) receiving FDA-approval from 1976-2011. In 2011, however, two new agents were FDA-approved for use in metastatic melanoma; ipilimumab, an anti-cytotoxic T-lymphocyte 4 monoclonal antibody, and vemurafenib, a BRAF inhibitor.

Melanoma harbour oncogenic BRAF mutations in 40-50% of cases. (Davies *et al.*, 2002) These mutations lead to constitutive activation of the BRAF kinase that then hyperactivates mediators of the mitogen activated protein kinase (MAPK) pathway including MEK and ERK. The ramifications of constitutive activation of the MAPK pathway include cell cycle dysregulation,

apoptosis resistance, immune evasion, and increased invasion and metastases. Further, patients with BRAF mutant melanoma have a worse prognosis than those without BRAF mutations. (Long *et al.*, 2012) Since the discovery that BRAF mutations are present in nearly half of all melanomas, strategies to develop therapeutic inhibitors have been underway. The first such agent to be associated with substantial clinical activity was vemurafenib. In the phase I study, it became clear early that treatment of patients with BRAF-mutant melanoma was associated with remarkable responses. (Flaherty *et al.*, 2010) In subsequent phase II and III studies, the activity of vemurafenib has been clearly established, objective response rates of approximately 50% and progression free survival of 6-7 months, and shown to be superior to treatment with chemotherapy in terms of response rate, PFS, and overall survival. (Chapman *et al.*, 2011; Sosman *et al.*, 2012) In May 2013, two additional agents, the BRAF inhibitor dabrafenib and the MEK inhibitor trametinib, were approved by the FDA for the treatment of melanoma based on Phase III studies showing superiority of single-agent treatment of each agent compared with chemotherapy. (Hauschild *et al.*, 2012; Flaherty *et al.*, 2012 #1) In January 2014, the combination of dabrafenib plus trametinib was approved based on data suggesting that combination therapy is better than single-agent BRAF inhibitor therapy. (Flaherty *et al.*, 2012 #2)

Oncogenic BRAF mutations are also seen across a number of other malignancies including 40-50% of papillary thyroid cancer, 10% of colorectal cancer, less than 5% of non-small cell lung cancer, and in lower percentages of other malignancies. BRAF inhibitor therapy has been tested widely in these diseases with variable results, and now dual BRAF/MEK inhibitor targeting is being tested. Specifically, responses have been seen with vemurafenib (Dadu *et al.* 2014) in nearly half of patients with BRAF-mutant papillary thyroid cancer, and there is an ongoing study evaluating the effectiveness of dabrafenib with or without trametinib in recurrent, BRAF-mutant recurrent thyroid cancer (NCT01723202). Additionally, there is a 12% response rate in BRAF-mutant colon cancer with the combination of dabrafenib and trametinib (Corcoran *et al.* 2014), and a number of clinical trials are looking to improve the efficacy of BRAF-targeted therapy in this subset of colon cancer patients (NCT01719380, NCT01750918, NCT01791309). Lastly, a number of reports are emerging detailing the responsiveness of BRAF-mutant lung cancer to single-agent BRAF inhibition. (Peters *et al.* 2013, Robinson *et al.* 2014)

2.2 CTEP Agents

2.2.1 Trametinib Dimethyl Sulfoxide (GSK1120212B)

The RAF-MEK-ERK pathway plays a critical role in multiple cellular functions. Activation of the pathway can result from activation/mutations of the upstream receptor tyrosine kinases (RTKs) and RAS, or upregulation/mutations in RAF and MEK. Upon activation, RAF acts as the MAPK kinase kinase and activates MAPKK (MEK1/2), which in turn catalyze activation of the effectors ERK1/ERK2. Once activated, ERK1/2 translocate into the nucleus and phosphorylate a number of effector proteins and transcriptional factors that regulate cell proliferation, motility, differentiation, and survival. Trametinib is one of the several MEK inhibitors in clinical development. Experience to date indicates that MEK is a valid target. In a phase III trial comparing trametinib with dacarbazine or paclitaxel in patients with BRAF V600E or V600K

mutant metastatic melanoma, trametinib demonstrated a significantly better response rate, progression-free survival, and overall survival (Flaherty *et al.*, 2012 #1). However, single agent activities are limited. Extensive research is underway to identify the patient selection markers and develop rational combination strategies. Preclinical studies have provided strong rationale and proof of principle for combination of MEK inhibitors with RTK inhibitors (EGFR or IGF-1R) (Gopal *et al.*, 2010; Ebi *et al.*, 2011), PI3K/AKT inhibitors (Engelman *et al.*, 2008; Hoeflich *et al.*, 2009), and mTOR inhibitors. On the other hand, the optimal dose/schedule and patient selection criteria for combination regimens have not been defined. Phase 1 results for a number of combinations have been reported, including AZD6244 + MK2206 (Tolcher *et al.*, 2011) and GDC-0973 + GDC-094 (MEK + PI3K inhibitor) (Bendell *et al.*, 2011).

2.2.1.1 Mechanisms of Action and Preclinical Data with Trametinib

Trametinib is a dimethyl sulfoxide (DMSO) solvate compound (ratio 1:1) with potent, allosteric and ATP non-competitive inhibition of MEK1/2 (IC₅₀ of 0.7 and 0.9 nM against MEK1 and MEK2, respectively) (Gilmartin *et al.*, 2011). Trametinib inhibited MEK1/2 kinase activity and prevented RAF-dependent MEK phosphorylation (S217 for MEK1), producing prolonged pERK1/2 inhibition. Trametinib showed better potency against unphosphorylated MEK1/2 (u-MEK1/2) when compared with preactivated diphosphorylated MEK (pp-MEK), suggesting that u-MEK affords a higher affinity binding site for trametinib than does pp-MEK.

The specificity of trametinib was confirmed against a panel of 183 kinases, including MEK5 (the closest kinase homolog to MEK1/2), CRAF, BRAF, ERK1, and ERK2 (Yamaguchi *et al.*, 2011). Trametinib demonstrated equal potency against activated MEK1- and MEK2-mediated phosphorylation of ERK (sequence identity of 85% across the whole protein and 100% in the active site for humans). Trametinib demonstrated preferential inhibition of RAF-mediated MEK1 activation (IC₅₀ = 0.60 nM) over pMEK1 kinase activity (IC₅₀ = 13 nM) (Investigator's Brochure, 2012a).

BRAF-mutant Colo205, A375P F11s, and HT-29 human tumor xenograft mouse models showed the most significant mean tumor growth inhibition (TGI) (80% to 87%) at 3.0 mg/kg trametinib, with multiple complete and partial tumor regressions. In the Colo205 model, tumor regression was observed even at a dose of 0.3 mg/kg (Yamaguchi *et al.*, 2011). Two KRAS-mutant xenograft models, HCT-116 and A549, also showed significant TGI (83% and 75%) but without significant tumor regressions (Gilmartin *et al.*, 2011). As predicted by cell proliferation assays, tumor xenograft lines with wild-type (wt) RAF/RAS (PC3, BxPC3, and BT474) were much less sensitive, showing only modest TGI (44-46%) with no tumor regressions.

Pharmacodynamic studies were performed in mice treated with trametinib for 14 days (Gilmartin *et al.*, 2011). In the A375P F11s xenograft model, the first dose of trametinib (3 mg/kg) significantly reduced pERK for more than 8 hours on Day 1. pERK inhibition was more sustained (over 24 hours) after the Day 7 dose, probably due to an increase in the steady-state levels of trametinib after repeated doses. The average C_{max} in blood was

1,410 nM on Day 7, with an estimated half-life ($t_{1/2}$) of 33 hours. In addition, immunohistochemistry (IHC) also confirmed inhibition of cell proliferation (reduced Ki67) and G1 cell cycle arrest (elevated p27Kip1/CDKN1B) following 4 days of treatment.

